7.1.7 Clinical Laboratory Safety Tests

Blood samples (up to 25 mL) will be collected for clinical laboratory safety tests at the timepoints specified in [Table 3](#) - SOA. A list of laboratory evaluations is provided in [Table 2: Clinical Laboratory Evaluations](#) below.

Table 2: Clinical Laboratory Evaluations

Haematology	Hematocrit	White blood cell (WBC) count
	Hemoglobin	WBC differential (absolute):
	Mean corpuscular hemoglobin	Basophils
	Mean corpuscular hemoglobin concentration	Eosinophils
	Mean corpuscular volume	Lymphocytes
	Platelet count	Monocytes
	Red blood cell (RBC) count	Neutrophils
	RBC distribution width	
Clinical Chemistry	Alanine aminotransferase (ALT)	Creatinine phosphokinase
	Albumin	Glucose
	Alkaline phosphatase	Phosphorus
	Aspartate aminotransferase (AST)	Potassium
	Calcium	Sodium
	Carbon Dioxide (CO ₂)	Total bilirubin
	Chloride	Total protein
	Creatinine	
COVID-19 Specific		At a minimum will be collected:
	eGFR	• Screening Visit
	Troponin	• Every 2 days during hospitalization
	CRP	• Discharge Visit
	Ferritin	• Day 28 Visit
	D-dimer	• Day 40 Visit
Other	Pregnancy Test (urine or serum)	To be performed for WCBP at Screening Visit
	Tumour Necrosis Factor (TNF)	To be collected: • Day 1 (before dosing with study drug)
	Anti-drug Antibody (ADA)	To be collected: • Day 1 (before dosing with study drug) • Day 28 Visit • Day 40 Visit

If laboratory evaluations are performed more than once a day as part of the routine management of hospitalized COVID-19 patients, the results from the first set of daily labs collected will be reviewed for this study and entered in the CRF.

Safety clinical laboratory samples will be analysed by the investigational site's local pathology laboratory.

The ADA test will be collected by the site and sent to the central laboratory for analysis. Instructions on collection, processing and preparation for shipment of central laboratory samples will be provided in the Central Laboratory Manual.

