9.5.2 Secondary Endpoints

Descriptive statistics will be provided for each secondary endpoint and reported by treatment group. Absolute values and changes in inflammatory markers as well as the WHO Ordinal Scale for Clinical Improvement collected each day in hospital will be presented by day and treatment group. Length of stay in index hospital will also be descriptively summarized. The number and percent of participants with the following will be summarized by treatment group:

- Have a 1 point, 2 point etc. increase/decrease in WHO Ordinal Scale
- All-cause mortality at any time within Day 28 visit
- Transfer to ICU level care within Day 28 visit
- Have a new onset of neurological disease within Day 28 visit
- Have evidence of new CHF or new MI requiring medical intervention within Day 28 visit
- Have new onset of embolus or thrombus within Day 28 visit
- Develop need for renal replacement therapy within Day 28 visit

Graphical presentation of endpoint data may be presented and will be described in the SAP.

The secondary estimand population for all secondary endpoints will be estimated based on the mITT population and includes randomized participants who have been diagnosed with COVID-19, have at least one co-morbidity, are admitted to the hospital and have pulmonary complications due to COVID-19 who receive any amount of study drug. To estimate this estimand, all post-randomization data up until Day 28 of the study will be used in the evaluation of each secondary endpoint. Specific handling of intercurrent events for each secondary estimand will be defined in the SAP.

The statistical analyses for secondary estimators with binary outcomes will be performed using CMH tests similar to the primary estimator. In addition, logistic regression analyses as described for the primary efficacy estimator may be performed. Treatment arm will be included in the model as well as age and number of co-morbidities at baseline as covariates. Parameter estimates, odds ratio and the corresponding 2-sided 95% CIs will be provided.

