3 STUDY DESIGN

3.1 General Description

The trial is a Phase 2, double-blind, placebo-controlled, randomized clinical trial of INB03 in participants with pulmonary complications from COVID-19 infection. Each participant will complete up to 6 study visits.

Screening: Participants with a diagnosis of COVID-19 will be screened for study eligibility. Prior to any trial related procedures, participants will provide their consent to participate in the clinical trial. Screening assessments that are performed as part of routine clinical care within 1 day of Screening do not need to be repeated.

Study Day 1: Eligible participants will be randomized to receive either INB03 at 1mg/kg by subcutaneous injection (SC) + standard of care (SofC) or Placebo SC injection + SofC within 1 day of Screening. Participants will receive their first dose of study drug after randomization. Blood samples to check TNF levels and perform an anti-drug antibody test will be collected before dosing. Clinical assessments while participants are inpatients will be as per routine management of hospitalized COVID-19 patients including daily collection of vital signs, physical exam, concomitant medications (including SofC) and laboratory evaluations. 12-lead ECGs and chest imaging assessments will be performed if deemed clinically necessary. Additionally, use of non-mechanical ventilation will be collected daily until the participant is discharged from hospital.

The WHO Ordinal Scale will also be completed daily until the participant is discharged from hospital.

Study Day 8: Participants will be given a second dose of INB03 or Placebo on Day 8 (7 days after randomization) if they remain in hospital. Clinical assessments while participants are inpatients will continue as per routine management of hospitalized COVID-19 patients.

Since the timing of hospital discharge in this patient population cannot be predicted, discharge assessments will be obtained on the day the participant is to be discharged. If the participant remains in the hospital, the participant will continue with daily assessments as per the Schedule of Assessments (SOA) (Table 3 in the protocol). At discharge, no additional follow-up is expected until the participant is seen for the Study Day 28 visit.

Study Day 28: A follow-up visit will be conducted on Day 28. If participant is still in hospital at Study Day 28, no additional follow-up is expected until the participant is seen on the Day 40 final safety visit.

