5.4 Visit Windows

In general, data will be summarized and listed using the recorded nominal visit values in the eCRF, regardless of the actual study day on which a value was collected. Unscheduled visits will not be summarized in tables but will be presented in data listings.

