6.2.2.1 Continuous Endpoints

Descriptive statistics will be provided for each endpoint and will be reported by treatment arm. Endpoints that are not normally distributed will also display geometric means. Absolute values and changes from baseline will be presented for the following:

- Inflammation markers (COVID-19 Specific markers: eGRF, Troponin, CRP, Ferritin, D-dimer)
- WHO Ordinal Scale for Clinical Improvement

Baseline will be defined as the value in the database prior to receiving any amount of study treatment. Line plots of means with error bars for the above endpoints will be presented by treatment group. Figures of means for both absolute values at each timepoint and the changes from baseline will be provided.

Changes from baseline will further be analyzed statistically using a mixed model repeated measures (MMRM) analysis. Factors include treatment arm, timepoint, age (≤ 50 , >50 to 65 , >65) and number of co-morbidities (1, 2, 3+). The baseline value of the endpoint will be included as the covariate. Patient will be repeated by timepoint. An unstructured covariance and the Kenward Roger's approximation for the degrees of freedom will be assumed. Least-square means will be provided for the treatment differences (INB03 + SofC vs Placebo + SofC) as well as the corresponding 95% CIs.

Descriptive statistics will be provided for the following endpoints and reported by treatment arm.

- Length of stay in index hospital
- Days to disease progression

Length of stay in index hospital will be derived as the index hospital discharge date – randomization date +1. Time will be considered in the derivation if collected for both dates. If discharge date is missing, date of death or end of study date will be used, whichever comes first.

Days to disease progression is not a specified secondary endpoint in the clinical study protocol, however is of interest to summarize. Days to disease progression will be derived as the first date of disease progression – randomization date +1. Intercurrent events, as defined in Section 6.2.1.3, will be considered when assigning a patient as having disease progression. Patients with no disease progression and who have completed the study will be censored as the duration on study. Patients who terminated the study early and with no disease progression according to Section 6.2.1.3 will be censored and given the longest duration, 40 days.

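### The SAP's nominal-visit default does not keep Discharge out of the marker and WHO-score timepoints, so values from different study days could be compared under one label

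*SAP*

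**What the plan says.** - **Default rule.** SAP 5.4 states, qualified by the words in general, that "data will be summarized and listed using the recorded nominal visit values in the eCRF, regardless of the actual study day".
- **Collection.** Protocol 7.1.7, Table 2, sets the minimum collection of eGFR, troponin, CRP, ferritin and D-dimer: Screening, "Every 2 days during hospitalization", "Discharge Visit", Day 28 and Day 40. Protocol 7.2.2 scores the WHO scale daily in hospital, at discharge, at Day 28 and at Day 40.
- **Timing of discharge.** SAP 3.1 says that "discharge assessments will be obtained on the day the participant is to be discharged", and that this timing cannot be predicted.
- **Analysis.** SAP 6.2.2.1 says that "Figures of means for both absolute values at each timepoint and the changes from baseline will be provided". It analyses change from baseline by MMRM: "Factors include treatment arm, timepoint, age" group and number of co-morbidities, with baseline as covariate and an unstructured covariance. It does not list the timepoints, does not mention Discharge, and lists no treatment-by-timepoint term.
- **Protocol counterpart.** Protocol 9.5.2 says that inflammatory markers and WHO scores "collected each day in hospital will be presented by day and treatment group". SAP 6.2.2.1 does not repeat this, and SAP 1.1 does not list it as a change.

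**The concern.** Discharge is an event, not a time. Under a nominal-visit rule, a value taken on Day 5 and one taken on Day 11 both become the Discharge value. Shorter hospital stay is itself a secondary objective (Protocol 3.2), so a comparison at Discharge may set the arms side by side at different times since dosing, and only among participants who were discharged. That does not estimate the endpoint as worded, which is change in the markers over time. A drug that affects only length of stay could appear to affect inflammation, and a drug that does reduce inflammation could appear not to.

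**Working it through.** The plan gives no figure to reproduce here, and the documents give no marker time course. The kinetics below are therefore assumptions, shown over a range.

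**1. What the text allows.** The SAP makes by-variable choices elsewhere. SAP 6.3.3 summarizes vital signs by study day. SAP 6.3.2 gives safety laboratory data as listings because collection dates may vary. SAP 6.3.6.3 collects SaO2 at discharge, among other times, and reports it at each timepoint of collection, so Discharge is a summary timepoint there. No such choice is written for the markers or the WHO score, which leaves the 5.4 default.

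**2. One worked pair.** Take two participants with the same CRP course: 100 mg/L at baseline, halving every 3 days. Discharged 4 days after baseline, the value is 100 × 2^(−4/3) ≈ 40 mg/L. Discharged at 10 days, it is 100 × 2^(−10/3) ≈ 10 mg/L. Both would enter the same Discharge mean.

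**3. Closed form.** Suppose the log marker falls by ln2/h per day in both arms (half-life h), and INB03 only brings discharge forward by s days. The log difference at Discharge is s·ln2/h, so the INB03/placebo ratio of geometric means is 2^(s/h).

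| Half-life | s = 1 day | s = 2 days | s = 3 days |
|---|---|---|---|
| 2 days | 1.41 | 2.00 | 2.83 |
| 3 days | 1.26 | 1.59 | 2.00 |
| 5 days | 1.15 | 1.32 | 1.52 |
| 10 days | 1.07 | 1.15 | 1.23 |
| rising, doubling in 10 days | 0.93 | 0.87 | 0.81 |

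A simulation with mean placebo discharge at about Day 8 agrees. For s = 2 it gives 1.96, 1.57, 1.31 and 1.14 for half-lives of 2, 3, 5 and 10 days.

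**4. Discharge triggered by the marker.** If participants leave when the marker reaches a fixed threshold, and INB03 speeds the fall by 30% or 60%, mean discharge moves from Day 8.59 to Day 6.84 or Day 5.74. The difference at Discharge is 0.00 in both cases, so a true effect is invisible there.

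**5. Size in a model with treatment as a main effect.** A second simulation, on log change from baseline, had inpatient values at Days 3 to 11 while in hospital, then Discharge, Day 28 and Day 40. Values could not fall below a floor, which makes the Discharge difference for h = 3 smaller than in step 3. The true marker effect was nil and s = 2. The fit assumed working independence rather than the full unstructured covariance.

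| Half-life | At Discharge | Pooled, with a Discharge label | Pooled, discharge values in study-day bins |
|---|---|---|---|
| 3 days | +0.389 | +0.073 | +0.008 |
| 5 days | +0.267 | +0.044 | +0.003 |

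The pooled bias is about one fifth of that at Discharge (0.389/0.073 = 5.3) or one sixth (0.267/0.044 = 6.1). With no shift in discharge, the pooled estimates lay between −0.006 and +0.008, so the last column cannot be told from zero.

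**6. At the size of this trial.** SAP 6.2.4 reports 77 participants dosed, about 38 per arm if split equally. With h = 3 and s = 2, a test made at Discharge alone gives nominal p < 0.05 against INB03 in about 0.51 of runs, against 0.03 with no shift (400 runs each). This applies only if a Discharge-specific contrast is tested, which the listed model factors do not call for.

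No calculation was made for the WHO score; the same rule applies to it, but its size is not quantified here.

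**The case against.** The strongest reply is that the SAP nowhere names Discharge as an MMRM timepoint. Section 5.4 is a general default, the SAP is to be read together with the protocol, and Protocol 9.5.2 already presents in-hospital values by day. The visit labels sit in the eCRF, which is not among the documents, and the schedule table cannot be read in this copy. All of this stands, so the point is what the text permits, not what will certainly be done. It does not close the gap: with a by-day rule in the protocol and a nominal-visit rule in the SAP, a programmer could follow either.

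A reader might infer more than the documents support:

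- **That INB03 would look worse.** This needs a marker that falls up to discharge and a discharge decision unrelated to its level; the documents state neither. For eGFR, worse means lower.
- **That a discharge after Day 28 puts the repeated measures in the wrong order.** With timepoint as a factor and an unstructured covariance, order does not affect the fit.
- **That data past Day 28 enter the endpoint.** SAP 6.2 and Protocol 9.5.2 limit efficacy data to Day 28, and no follow-up is expected between Day 28 and Day 40 for those still in hospital.

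It is also fair that study-day means have a selection problem of their own: they describe only those still in hospital that day, and earlier discharge changes who remains. The simulations made discharge independent of the marker in the time-only scenarios, so they do not test this.

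**Conclusion.** The concern holds in a conditional form. As written, the plan allows Discharge to serve as one timepoint for the markers and the WHO score, mixing study days under a label whose timing is an expected treatment outcome, and it does not reconcile this with Protocol 9.5.2.

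For markers that fall with half-lives of 2 to 5 days, discharge 2 days earlier and no marker-based discharge decision, the spurious ratio at Discharge is about 1.3 to 2.0. It falls below 1 for a rising marker. If discharge is marker-triggered, a real effect can disappear. In a main-effect model the distortion is small, about +0.07 log units for a 3-day half-life, so the means and plots at Discharge are the more exposed outputs. The SAP does not state a log transformation for the MMRM, so the log-scale results show direction and relative size rather than a bias in the units of the planned analysis.

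The endpoints affected are secondary, with nominal p-values and no multiplicity control, and the primary endpoint does not use the marker values. The change is worth making, but it does not threaten the main conclusion of the trial.

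**What to change.** In SAP 5.4 and 6.2.2.1, in line with Protocol 9.5.2:

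1. Assign inpatient and discharge marker and WHO values to the actual study day, or to fixed windows built on the every-2-days marker schedule. State the reference date (SAP 5.2 gives the Study Day formula with a generic one) and which record is used when two fall in the same window.
2. List the timepoints that enter the MMRM.
3. Do not use Discharge as a timepoint in means, plots or the MMRM.
4. Keep discharge values in listings, or in a descriptive table that also shows the day of discharge.

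The cost is a few lines of SAP text and a small derivation from assessment dates, which SAP 5.1 already uses to sort listings. No new data are needed. Make the change before marker data are seen by arm. One limitation remains and should be stated with the results: study-day means in hospital reflect only the participants still there.

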5.5 Pooling of Sites

Sites will be pooled for all analyses.

6 ANALYSIS METHODS

6.1 Study Patient Data

6.1.1 Patient Enrollment and Disposition

The number and percentage of patients in each analysis population and final patient status (completed or withdrawn), including reasons for withdrawal, will be produced based on the number of randomized patients. In addition, the number of patients receiving 1 or 2 doses of study treatment will be presented. Data will be presented by treatment arm and overall. Patients who were enrolled and not randomized will be included in the overall column.

Patients contributing to each analysis populations and final patient disposition status will be listed.

6.1.2 Protocol Deviations

Protocol deviations will be identified and classified as minor or major (violations) before the database is locked. Major protocol deviations include and are not limited to:

- Violation of Inclusion/Exclusion Criteria
- Signed incorrect version of patient consent form
- Use of prohibited therapies
- Receiving incorrect randomized treatment
- Did not receive mechanical ventilation due to the machine not being available

Each protocol deviation will be reviewed prior to database lock and the deviations that are identified as having an impact on the primary study endpoint will be flagged and patients with those deviations will be excluded from the PP population.

Protocol deviations will be summarized by treatment arm and overall for the study.

A listing of protocol deviations will be provided.

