9.3.3 Per-Protocol Set (PPS)

All participants included in the ITT population with no major protocol deviation will comprise the PPS. The PPS will be a secondary analysis population for select efficacy endpoints. Analyses will be based on treatment received.

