3.3 Sample Size

A total sample size of 366 participants randomized 1:1 to treatment with either INB03 + SofC or Placebo + SofC (N=183 in each arm) will provide adequate power to compare the proportion of participants with disease progression in each group by Day 28. It is assumed that 21% of enrolled participants randomized to Placebo + SofC will progress whereas the expected disease progression rate will be reduced by two-thirds to 7% in participants randomized to INB03 + SofC. To observe the expected treatment effect, N=346 (N=173 per arm) are required.

Additionally, an interim analysis for futility will be performed once approximately 20% of participants required to observe the expected treatment effect complete the Study Day 28 visit (approximately N=70). Participants evaluated in the interim analysis include those who are randomized and receive study drug and have the Day 28 assessment or who had an intercurrent event prior to Day 28. A customized futility boundary was chosen to ensure a clinically meaningful difference between treatment arms is observed at the interim and which will provide a high conditional power at the time of the final analysis.

The proposed study with the above assumptions will have at least 90% power assuming a one-sided Z-Test with overall alpha for the study of 0.005.

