4 ANALYSIS POPULATIONS

Intent-to-treat (ITT) Population: All participants who have signed informed consent, meet inclusion/exclusion criteria, are enrolled in the study and who are randomized to a treatment arm will be included in the ITT population. The ITT will be the analysis population for disposition and demographic reporting purposes. Analyses will be based on the randomized treatment.

Modified Intent-to-treat (mITT) Population: The modified ITT population is a subset of the ITT population and includes participants who have received any amount of INB03 or Placebo. The mITT will be the primary analysis population for all efficacy reporting purposes. Analyses will be based on the randomized treatment.

Per-protocol (PP) Population: All participants included in the mITT population with no major protocol deviation will comprise the PP population. The PP population will be a secondary analysis population for select efficacy endpoints. Analyses will be based on treatment received. Protocol deviations and assignment to the PP population will be done prior to unblinding.

Safety Population (SAF): All participants who have received any amount of INB03 or Placebo are included in the safety set. The SAF will be the analysis population for safety reporting and will be based on treatment received (INB03 or Placebo).

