6.2.1.5 Supportive and Supplemental Analyses

The primary analysis will be repeated using the PP population. The strategies considered for handling intercurrent events will be the same in this analysis as for the primary analysis in the mITT population.

A supportive analysis will be performed on the primary endpoint using a logistic regression analysis model with treatment group and continuous covariates of age at baseline and number of co-morbidities at baseline included in the model as covariates. Parameter estimates, odds ratio and the corresponding 95% CIs will be provided. The strategies for handling intercurrent events will be the same in this analysis as for the primary analysis, and the population for analysis will be the mITT population.

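### The per-protocol set has three conflicting definitions, and its exclusions overlap with intercurrent events that the primary estimand keeps in the analysis

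*SAP*

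**What the plan says.** Three places define who is in the PP set.

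- Protocol 9.3.3: "All participants included in the ITT population with no major protocol deviation will comprise the PPS". The set is analysed by treatment received.
- SAP 4: "All participants included in the mITT population with no major protocol deviation will comprise the PP population". This is also by treatment received, with membership assigned before unblinding.
- SAP 6.1.2: deviations are reviewed before the database is locked. The rule for exclusion reads: "the deviations that are identified as having an impact on the primary study endpoint will be flagged and patients with those deviations will be excluded".

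SAP 1.1 lists changes from the protocol but not the move from ITT to mITT as the base of this set.

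The major deviations named in SAP 6.1.2 include use of prohibited therapies and this item: "Did not receive mechanical ventilation due to the machine not being available". SAP 6.2.1.1 treats the same two occurrences as intercurrent events, with a treatment-policy strategy for prohibited medication and a hypothetical strategy for ventilator unavailability. SAP 6.2.1.5 repeats the primary analysis in the PP population and adds: "The strategies considered for handling intercurrent events will be the same in this analysis as for the primary analysis in the mITT population".

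**The concern.** Two participants with the same record can be in or out of the PP set depending on which section the programmer follows, and two of the three rules sit in the same SAP.

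The ventilator item is a selection problem. Nobody can go without a ventilator for lack of a machine until they need one, and the SAP endpoint is the development of that need, or death. Excluding such a participant conditions the PP analysis on the outcome. Prohibited therapy is also a post-randomization event. Its use may be related to worsening disease, although the documents give neither its frequency nor its timing.

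If these participants are excluded, the two strategies that SAP 6.2.1.5 carries over have nobody to act on. SAP 1.1 has already dropped the ITT analysis, so the PP repeat is the only remaining analysis of the primary endpoint in another population. If its membership is unclear or depends on outcome, it is a weak check on the mITT result.

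**Working it through.** **Step 1. Membership rules side by side**

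| Place | Base set | Excluded |
|---|---|---|
| Protocol 9.3.3 | ITT | any major deviation |
| SAP 4 | mITT | any major deviation |
| SAP 6.1.2 | not restated | only deviations flagged as affecting the primary endpoint |

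Signing the wrong consent version is a listed major deviation. That participant is out under SAP 4 but stays in under SAP 6.1.2 unless flagged. The protocol's base set can also hold undosed participants, who have no treatment received to be analysed by. SAP 6.2.4 reports 79 randomized and 77 dosed, so at most 79 − 77 = 2 people are affected.

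**Step 2. Is a participant who needed a ventilator but could not get one an event?**

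- SAP 6.2.1 and 6.2.1.1 count the need for ventilation, or death: event.
- The estimator in protocol 9.5.1 counts administration of ventilation, or death: no event unless the participant dies or is ventilated later.
- SAP 6.2.1.3, when endpoint data are missing, uses the last WHO score before the occurrence and gives no cut-off. Protocol 9.5.1 uses 7 or higher for its own missing-data cases. On that cut-off a last score of 5 or 6 is a non-event unless death is recorded.

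Exclusion therefore removes an event under the SAP's need definition, and under any reading if the participant died by Day 28. On the other readings it may remove a non-event, which would raise that arm's rate.

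**Step 3. The plan's own figure**

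SAP 3.3 states: "It is assumed that 21% of enrolled participants randomized to Placebo + SofC will progress". The INB03 rate is 7% with 173 per arm, and the study "will have at least 90% power", "assuming a one-sided Z-Test with overall alpha for the study of 0.005".

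Unpooled normal approximation: n = (2.576 + 1.282)² × (0.21×0.79 + 0.07×0.93) / 0.14² = 14.88 × 0.2310 / 0.0196, or 176 per arm. The arcsine formula gives 172. Power at 173 per arm is 0.895 (unpooled) or 0.885 (pooled). The stated size is reproduced closely enough and is not in dispute.

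**Step 4. What exclusion does to the effect**

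Let a be the fraction of progressors excluded and b the fraction of non-progressors. In each arm:

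- PP rate = p(1−a) / [p(1−a) + (1−p)(1−b)]
- PP odds = p/(1−p) × k, with k = (1−a)/(1−b)
- PP odds ratio = true odds ratio × k(INB03)/k(placebo)

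The true odds ratio at the planning rates is (0.07/0.93)/(0.21/0.79) = 0.283. The fractions below are assumptions, with b = 0, 173 per arm before exclusion and pooled power.

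| a, placebo / INB03 | Rates | Risk difference (points) | Odds ratio | Power |
|---|---|---|---|---|
| 0 / 0 | 21.0% vs 7.0% | −14.0 | 0.283 | 0.885 |
| 10% / 10% | 19.3% vs 6.3% | −13.0 | 0.283 | 0.85 |
| 20% / 20% | 17.5% vs 5.7% | −11.9 | 0.283 | 0.80 |
| 30% / 30% | 15.7% vs 5.0% | −10.7 | 0.283 | 0.74 |
| 30% / 10% | 15.7% vs 6.3% | −9.3 | 0.364 | 0.57 |
| 0 / 20% | 21.0% vs 5.7% | −15.3 | 0.227 | 0.95 |

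With no true effect (21% in both arms), excluding no placebo events and 30% of INB03 events shows 21.0% vs 15.7%, odds ratio 0.70.

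**Step 5. At the size reached**

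With 77 dosed, about 38.5 per arm, expected events are 38.5 × 0.21 = 8.1 and 38.5 × 0.07 = 2.7. Pooled power is about 0.21 before any exclusion. As an illustration, assume a 38/39 split with 8 placebo and 3 INB03 events:

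- No exclusion: (3/36)/(8/30) = 0.31
- One INB03 event excluded: (2/36)/(8/30) = 0.21
- Two placebo events excluded: (3/36)/(6/30) = 0.42

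**The case against.** The PP repeat is supplemental. Primary inference uses mITT, keeps prohibited-drug users under treatment policy, and has its own tipping-point analysis. Excluding prohibited-therapy users from a PP set is conventional. Under SAP 6.1.2 a listed deviation leads to exclusion only if flagged, and the other intercurrent-event strategies (withdrawal, loss to follow-up, missed second dose, other discontinuation) still apply in the PP set. With 77 of 79 dosed, the choice of ITT or mITT as base moves at most two people. All of this stands and limits the weight of the point.

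Stronger readings are tempting, and the documents do not support them.

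- A reader might infer that the PP set drops everyone who needed a ventilator. The item covers only those who went without because no machine was available. Participants who were ventilated stay in and count as events, absent another excluding deviation.
- A reader might infer that prohibited drugs stand for rescue use and that excluding users deletes events. Protocol 6.6.1 only lists the drugs. A user is a lost event only if he or she also progressed.
- A reader might infer that exclusion always shrinks the effect, or costs a definite amount of power. Exclusion that is equal across arms leaves the odds ratio unchanged. The power losses above rest on assumed fractions at 173 per arm, a size the trial did not reach.

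None of this reconciles the three rules, or the exclusion of participants whom SAP 6.2.1.5 says are handled by a stated strategy.

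**Conclusion.** The point holds as a conflict of definitions with a limited route to bias. The PP set has three incompatible rules, one change of base set is unrecorded, and the ventilator-unavailable exclusion contradicts SAP 6.2.1.5 and can remove an event under the SAP's need endpoint. The mITT primary analysis is untouched.

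The size cannot be read from the documents, because no deviation rates are given. If exclusion of progressors relative to non-progressors is the same in both arms, the risk difference shrinks and power falls while the odds ratio is unchanged. If it differs by arm, the odds ratio is biased in either direction. At the enrolment reached, one or two exclusions could move the PP odds ratio materially, assuming events occur at the planning rates. The correction should be made because this is the only alternative-population analysis left and it needs only wording.

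**What to change.** - State one PP definition, identically in SAP 4 and 6.1.2: mITT participants without any deviation on a closed list, such as an eligibility violation or incorrect treatment at either dose.
- Fix the list and the membership before any unblinded analysis. SAP 4 assigns membership before unblinding, SAP 6.1.2 reviews deviations before lock, and the preliminary unblinded analysis in SAP 6.2.4 also precedes final lock, so the timing needs one statement.
- Remove ventilator unavailability from the PP exclusions so that its stated strategy applies. Continue to report it as a deviation.
- For prohibited therapy after dosing, either keep those participants under treatment policy or say in SAP 6.2.1.5 that they are excluded. Either is defensible if the sections agree.
- Reconcile need with administration of ventilation across protocol 9.5.1 and SAP 6.2.1, 6.2.1.1 and 6.2.1.3, and state in the SAP the WHO score that counts as progression.
- Record the departure from protocol 9.3.3 in SAP 1.1.

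The cost is SAP wording and no new data. The PP set becomes larger and closer to mITT, so it offers less contrast with the primary analysis.
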